8. STATISTICAL METHODOLOGY AND STATISTICAL ANALYSES

8.1. Statistical Methods

8.1.1. Analyses for Continuous Data

8.1.1.1. Time-to-Event Endpoints

Time-to-event endpoints will be summarized by treatment group with the number of subjects at risk, the number and percentage of subjects with events, and event rates with 95% confidence intervals. Event rates will be calculated as the number of events per 100 subject-years at risk. The 95% confidence intervals will be calculated using an exact Clopper-Pearson method for Poisson random variables.

For the primary endpoint and the key secondary composite endpoint of cardiovascular death, non-fatal MI and non-fatal stroke, the number and percent of each component that occurs first will be summarized by treatment group. Events which occur on the day of, or the day after, the earliest event will be considered, and the following hierarchy will be applied:

1. CV Death,
2. Non-fatal MI,
3. Non-fatal stroke,
4. Hospitalization for unstable angina (if applicable).

For the primary endpoint and the key secondary composite endpoint of cardiovascular death, non-fatal MI and non-fatal stroke, the reasons for censoring will be summarized by treatment group.

Log rank test

Time-to-event endpoints will be tested with a log rank test stratified by geographic region and complete statin intolerance, and the two sided p-value from the stratified log rank test will be reported.

The log rank test is a non-parametric test of the equality of two distributions that allows for stratification and incorporates information about censoring. Stratification permits different event rates in different strata. The log rank test assumes that the censoring function is independent of the hazard function.

Cox proportional hazards regression

A Cox proportional hazards regression model for each endpoint other than time to discontinuation from therapy will be fit in the FAS with treatment group as a covariate and geographic region and complete statin intolerance as stratification factors. For time to all-cause death and time to discontinuation from study therapy, the Cox proportional hazards model will be fit in the SAS with the same covariate and stratification factors. If the model fitting fails to converge, complete statin intolerance will be removed as a stratification factor. The hazard ratios with corresponding 95% confidence intervals will be reported.

Cox proportional hazards regression is a semiparametric method for comparing hazard functions under the assumption of proportional hazards. The methodology can include adjustments for covariates for important prognostic factors, produces a point and interval estimate of the treatment effect, and allows for different baseline hazard functions in different strata to reflect different event rates in different strata. The methodology assumes that the censoring function is independent of the hazard function.

The goodness of fit of the Cox proportional hazards regression models for the primary endpoint and key secondary composite endpoint of cardiovascular death, non-fatal MI or non-fatal stroke will be assessed by plots of the cumulative expected number of events

(estimated cumulative hazard rates) versus the observed cumulative number of events for each treatment arm within each stratum formed by the combination of the two stratification factors, using the method proposed by Arjas (1988). Departures from straight lines indicate a departure from proportional hazards, which may or may not affect the interpretability of the treatment effect.

Kaplan-Meier estimates

Kaplan-Meier estimates of time to first event will be plotted for the primary endpoint, the key composite secondary endpoint of cardiovascular death, non-fatal MI and non-fatal stroke, and for all-cause death.

Kaplan-Meier estimates are non-parametric estimates of the distribution of time to first event that incorporates information about censoring. The methodology assumes that the censoring function is independent of the hazard function.

Multiple imputations for Cox proportional hazards regression

The impact of informative censoring on the primary analysis will be evaluated through multiple imputations. Imputation will only be done for surviving subjects who discontinued from the study prematurely and did not have a primary endpoint event. Several imputation models for informative censoring will be used. The Weibull distribution will be used to generate the imputed values.

Multiple imputation is a flexible technique for incorporating the uncertainty in missing data that is ignored by single imputation methods, such as LOCF or worse case imputation. The imputation model need not be identical to the analysis model, which enables the exploration for different departures from MAR. It permits the use of standard software to be used to analyze each imputed data set under intention to treat. The results of the individual analyses are then combined into a single result using standard techniques (Rubin, 1987).

The Weibull distribution with shape parameter λ and scale parameter θ has a hazard function of the form $\lambda t^{\lambda-1}/\theta^\lambda$, which can accommodate both increasing and decreasing hazard functions.

8.1.1.2. Other Continuous Endpoints

Other continuous endpoints will be summarized by visit and treatment group using descriptive statistics, including the mean, standard deviation, median, first and third quartiles (Q1 and Q3, respectively), and minimum and maximum.

Mixed model for repeated measures

Percent changes from baseline in all lipid endpoints and hs-CRP, and nominal changes from baseline in LDL-C will be analyzed using a mixed model repeated measures (MMRM) model with fixed effects for treatment (categorical variable), scheduled visit time point (categorical variable), baseline value (continuous variable), interaction between baseline value and scheduled visit time point, interaction between treatment and scheduled visit time point, and geographic region (categorical variable), and complete statin intolerance (categorical variable).

Restricted Maximum Likelihood (REML) estimation will be used, and the default covariance structure will be unstructured. Due to the slow onset of accrual in this event-driven trial, there will be few observations at the last several time points. One or more of the last visits may be removed to ensure convergence of the model fitting. Also, the geographic region with the fewest observations may be combined with the next smallest region to ensure convergence of the model fitting. This may be done twice. If the model fails to converge with an unstructured covariance matrix, a spatial power covariance will be used. If the model fails to converge with this covariance structure, compound symmetry will be used. Kenward-Roger degrees of freedom will be used. Estimates of treatment group means and mean treatment group differences using observed margins at Week 14 and each other visit, corresponding 95% confidence intervals, and p-value for the mean differences will be provided. The least-squares mean treatment group estimates and 95% confidence intervals will be plotted longitudinally.

For observed values of selected highly skewed circulating biomarker endpoints that are measured at more than one post-randomization visit, the same model will be fit in the same manner for log-transformed data. The data will be log-transformed prior to calculating changes. Any zero values will be replaced with 0.0001 to enable taking the logarithm. The estimated treatment group means using observed margins and corresponding 95% confidence intervals from the analysis of the log-transformed data will be transformed to percent changes for reporting. The estimated treatment group differences will be transformed to the ratio of the mean percent changes and reported with transformed 95% confidence intervals along with untransformed p-values. The transformed estimated mean percent changes and corresponding transformed 95% confidence intervals will be plotted.

Changes from baseline in cognitive test results, including the Digit Span Forward score, Digit Span Backward Score, Digit Symbol - Coding score, Trail Making A score, Trail Making B score, HVL T Total Recall score, HVL T Delayed Recall Trial score, and the HVL T Recognition score will be analyzed using an MMRM model with fixed effects for treatment (categorical variable), scheduled visit time point (categorical variable), baseline value (continuous variable), interaction between baseline value and scheduled visit time point, and interaction between treatment and scheduled visit time point.

MMRM incorporates information from multiple visits and allows for covariate adjustment of the treatment effect so as to take important prognostic factors into account. Both of these increase the precision of the estimates and the power of the tests.

MMRM is a recommended approach for confirmatory trials (Mallinckrodt et al., 2008). The MMRM analysis is unbiased under the assumption that all missing data are either missing completely at random (MCAR) or missing at random (MAR) and is often robust to departures from MAR. Siddiqui, Hung, and O'Neill (2009) have shown that under various null and alternative hypotheses, the MMRM analysis estimates the true treatment group difference at the study endpoint with negligible bias even in the presence of a 1:1:1 mixture of MCAR, MAR, and missing not at random (MNAR) missing data mechanisms.

Analysis of Covariance

Continuous measurements assessed at a single post-randomization time point (i.e., the percent changes from baseline to last non-missing post-baseline measurement in LDL-C) will be analyzed using an analysis of covariance model with treatment group and baseline value as covariates and geographic region and complete statin intolerance as factors. Kenward-Roger degrees of freedom will be used. Least squares means with corresponding 95% confidence intervals, the least-squares mean differences and corresponding 95% confidence intervals, and p-values will be presented.

ANCOVA allows for covariate adjustment of the treatment effect, increasing the precision of the estimates and the power of the tests. As a likelihood method, ANCOVA provides unbiased estimates under the MAR assumption.

8.1.2. Analyses for Categorical Data

Categorical endpoints will be summarized by treatment group with the number and percent of subjects at risk in the treatment group within each category.

8.1.3. Analyses for Binary Endpoints

For the differences between treatment groups in the percent of subjects with each Tier-1 AE, an exact method for producing 95% confidence intervals and p-values will be used (Chan and Zhang, 1999). The method is based on inverting two one-sided tests at half the significance level each. As an exact method, it is appropriate for rare events.

For the differences between the treatment groups in the percent of subjects with each Tier-2 AE, an asymptotic method for producing 95% confidence intervals as presented by Miettinen and Nurminen (1985) will be used. As an asymptotic method, it is appropriate for events that are not rare.

8.2. Statistical Analyses

Efficacy analyses, unless otherwise indicated, will be performed according to the intention-to-treat (ITT) principle. Unless otherwise indicated, all efficacy analyses will be done in the FAS.

The Safety Analysis Set (SAS) ... will be used for all safety analyses, unless otherwise specified.

8.2.1. Analysis of Primary Endpoint

The primary objective is to demonstrate superiority of bococizumab over placebo with respect to the primary endpoint, the time from randomization to the first adjudicated and confirmed occurrence of a major cardiovascular event, a composite endpoint which includes CV death, non-fatal MI, non-fatal stroke, and hospitalization for unstable angina needing urgent revascularization (as defined in [Appendix 1.2](#)). Subjects who discontinue randomized study medication prematurely and have not withdrawn consent will continue to be followed in the study to assess the occurrence of endpoints. Subjects who do not experience any of the components of the primary endpoint will be censored on the date of last contact or

01 November 2016, whichever comes first. The date of last contact is defined as the date of death, if the date is not missing. Otherwise, the date of last contact is defined as the study discontinuation date, the date of last visit, the date of last telephone contact, the onset date of the last AE, or the randomization date, whichever occurs last.

Primary analysis

The primary endpoint will be analyzed in the FAS using a log rank test stratified by geographic region and complete statin intolerance. The overall alpha level for this trial is 0.05. The two-sided alpha level for this log rank test will be adjusted for DMC reviews of all-cause death (see [Section 3](#)) and the interim analysis for clinical benefit (see [Section 3](#)) so that a two-sided alpha of 0.04898 will be used.

Analyses supportive of the primary analysis

A Cox proportional hazards model will be fit with the treatment group as a covariate and geographic region and complete statin intolerance as stratification factors. If the model fitting fails to converge, complete statin intolerance will be removed as a stratification factor. The hazard ratio will be presented along with a 95% confidence interval. The goodness of fit of the Cox proportional hazards regression model will be assessed by visual inspection of Arjas plots. Kaplan-Meier estimates of time to first major cardiovascular event will be plotted.

Sensitivity analyses

It is assumed that there will be a premature study discontinuation rate of 1% per year.

In order to aid in the assessment of the impact of premature discontinuation from the study on the primary analysis, time from randomization to premature discontinuation from the study will be analyzed. The p-value from a log rank test stratified by geographic region and complete statin intolerance will be presented. A Cox proportional hazards model will be fit with treatment group as a covariate and geographic region and complete statin intolerance as stratification factors. If the model fitting fails to converge, complete statin intolerance will be removed as a stratification factor. The hazard ratio and a 95% CI will be presented.

The impact of informative censoring on the primary analysis of the primary endpoint only will be evaluated through multiple imputations. Imputation will be done for all surviving subjects who were administratively censored and did not have a primary endpoint event. Separate imputation models will be fit for subjects on bococizumab and subjects on placebo. Imputation for both bococizumab and placebo subjects will use the placebo imputation model under the conservative assumption of switch-to-control risk following premature discontinuation from the study.

Weibull regression models will be fit separately by treatment group. Following Rubin (1987), a completed imputed data set will be generated in two stages. First, parameters for the Weibull model will be generated from a multivariate normal distribution with mean equal to the maximum likelihood estimates (MLE) of the parameters, and the variance-covariance matrix equal to the variance-covariance matrix of the MLE. Second, the Weibull

distribution based on the generated parameters will be used to simulate a time to event for each subject requiring imputation conditional on the time of censoring, appropriate treatment group, and baseline age, gender, body mass index, geographic region, baseline smoking status, complete statin intolerance, baseline history of MI, baseline history of coronary revascularization, baseline history of coronary heart disease, baseline history of diabetes (Type I or Type II), baseline history of heFH or LDL-C \geq 190 mg/dL, baseline history of stroke, baseline history of congestive heart failure and baseline history of chronic kidney disease.

If an imputed time to event would put the event date after 01November2016, the event will be censored and the imputed event time will be truncated so that the time to event is on 01November2016.

The completed data sets will be analyzed with the Cox proportional hazards model used for the primary analysis. This will be repeated for 100 data sets and the estimates of the log hazard ratio and their standard errors will be combined to form point estimates and confidence intervals using standard multiple imputation methodology (Rubin, 1987). The MI-based estimates and their confidence intervals will then be back-transformed to the hazard ratio scale. The estimated hazard ratio and a 95% confidence interval will be reported.

The reasons for censoring for the primary endpoint will be summarized by treatment group.

Supplemental analyses

Investigator-reported potential primary endpoint events will be listed.

The number and percent of each component of the primary endpoint that occurs first will be summarized by treatment group.

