- Lithuania and the Philippines were deleted from the appropriate geographic regions and the study was not conducted in those countries (Section 6.4).
- The definition of the date of last contact was modified to include the date of last visit and the date of last telephone contact. The former change was for the sake of completeness; the latter in response to a change in the Case Report Form (Section 7).
- The definition of missing values for the Digit Span Forward and Digit Span Backward was added (Section 7).
- Guidance for handling of missing values for the PHQ-2 and PHQ-9 was added (Section 7).
- Strategies for attaining convergence of MMRM model fitting were expanded (Sections 8.1.1.2, 8.2.2, and 8.2.3).
- It was clarified that estimation in MMRM models would use observed margins (Sections 8.1.1.2, 8.2.2, and 8.2.3).

- Summaries of the first component of the composite endpoint events were added for the primary endpoint and the composite secondary endpoint of cardiovascular death, non-fatal MI and non-fatal stroke. (Sections 8.2.1 and 8.2.2). The definition of the first component was added (Section 8.1.1.1).
- Multiple imputations for the primary endpoint were modified to impute for all subjects who discontinued from study prior to the date of program discontinuation and did not have a primary endpoint event from subjects who withdrew consent to be followed (Section 8.2.1).
- As a result of recent feedback on other trials, the sensitivity analyses were modified to remove the imputation based on the MAR assumption (Section 8.2.1).
- The sensitivity analysis involving multiple imputation for subject who report a targeted medical event associated with the mechanism of action of bococizumab was deleted, as it does not add value of the existing multiple imputation for subjects who discontinue the study due to an adverse event (Section 8.2.1).
- The tabulation of Adjudication Committee confirmation of suspected primary and secondary endpoint events by investigator evaluation and treatment group according to sponsor standards was removed and was replaced by a listing (Sections 8.2.1 and 8.2.2).
- The summaries of the component that occurs first for the primary endpoint and composite endpoint of cardiovascular death, non-fatal MI or non-fatal stroke were added (Sections 8.2.1 and 8.2.2).

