8.2.5. Summary of Efficacy Analyses

Table 2. Tabular Summary of Efficacy Analyses

Endpoint	Analysis Set	Statistical Method	Covariates/ Strata	Objective
Time to major cardiovascular event	FAS	Log rank test	Geographic region, complete statin intolerance	Primary analysis
		Cox proportional hazards regression	Treatment group/ geographic region, complete statin intolerance*	Decision on primary objective
		Plot of Kaplan-Meier Estimates		Support of primary objective
		Arjas plot	Geographic region × complete statin intolerance	
Time to premature discontinuation from the study	FAS	Log rank test	Geographic region, complete statin intolerance	Impact of premature discontinuation from the study
		Cox proportional hazards regression	Treatment group/ geographic region, complete statin intolerance*	
Time to major cardiovascular event	FAS	Multiple imputations for Cox proportional hazards model	Cox model: Treatment group/geographic region, complete statin intolerance* Imputation model: Treatment group set equal to placebo for all subjects, age, gender, BMI, geographic region, complete statin intolerance, baseline smoking status, baseline history of MI, baseline history of coronary revascularization, baseline history of coronary heart disease, baseline history of diabetes, baseline history of heFH/LDL-C \geq 190 ml/dL, baseline history of stroke, baseline history of congestive heart failure baseline history of chronic kidney disease.	Impact of informative censoring under the switch-to-control assumption

Endpoint	Analysis Set	Statistical Method	Covariates/ Strata	Objective
Time to CV death, non-fatal MI or non-fatal stroke	FAS	Log rank test	geographic region, complete statin intolerance	First key secondary endpoint; tested only if the primary objective is met
		Cox proportional hazards regression	Treatment group/ geographic region, complete statin intolerance*	Decision on secondary objective
		Plot of Kaplan-Meier Estimates		Support of key secondary objective
		Arjas plot	Geographic region × complete statin intolerance	
Time to all-cause death, non-fatal MI, non-fatal stroke, or hospitalization for unstable angina needing urgent revascularization	FAS	Log rank test	Geographic region, complete statin intolerance	Second key secondary endpoint; tested only if the primary objective is met
		Cox proportional hazards regression	Treatment group/ geographic region, complete statin intolerance*	Decision on secondary objective

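### The SAP gives two different populations for the informative-censoring imputation; on the usual meaning of its wording in 8.2.1, the analysis changes nothing

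*SAP*

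**What the plan says.** Two current sections of the SAP describe the same multiple imputation of the primary endpoint, and each says who is imputed.

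- Section 8.1.1.1 (methods): "Imputation will only be done for surviving subjects who discontinued from the study prematurely and did not have a primary endpoint event".
- Section 8.2.1 (sensitivity analyses): "Imputation will be done for all surviving subjects who were administratively censored and did not have a primary endpoint event".

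Section 8.2.1 applies the placebo imputation model to both arms, "under the conservative assumption of switch-to-control risk following premature discontinuation from the study". It uses the fitted Weibull distribution to "simulate a time to event for each subject requiring imputation conditional on the time of censoring", and then truncates: "If an imputed time to event would put the event date after 01November2016, the event will be censored".

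Table 2 in section 8.2.5 gives the purpose as "Impact of informative censoring under the switch-to-control assumption" and names no population. Section 7 and section 8.2.1 censor event-free subjects at the earlier of last contact and 01 November 2016. Neither of those two dates is labelled administrative.

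**The concern.** One section restricts the imputation to early leavers. The other applies it to everyone in a class that the SAP never defines. In ordinary usage, administrative censoring means that follow-up was complete and event-free when the data were cut. That group does not overlap with premature discontinuers, and it does not fit the rationale in 8.2.1 itself, which concerns risk after leaving the study.

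This is the only analysis in 8.2.1 that re-estimates the primary hazard ratio under informative censoring. The time-to-discontinuation analysis and the summary of reasons for censoring remain, but neither gives an alternative hazard ratio. A programmer who followed 8.2.1 on the ordinary meaning would report a result identical to the primary Cox model under an informative-censoring label. If the wording is still open when the data are unblinded, the population becomes a post-hoc choice.

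**Working it through.** **Step 1. The ordinary reading of 8.2.1.** Let *c* be a subject's time from randomization to 01 November 2016. If the subject is event-free and censored at *c*, the imputed time *T\** is drawn given *T\** > *c*. The truncation rule then records min(*T\**, *c*) = *c* with no event, which is the original record. All 100 completed data sets are the same as the observed one, the between-imputation variance is zero, and Rubin's rules return the primary Cox hazard ratio and interval. This needs no numerical assumption.

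**Step 2. Planning inputs for the other reading.**

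- 11,000 subjects 1:1, 2.7% per year event rate (taken as the placebo rate, as in Protocol 9.1.2), hazard ratio 0.75, 508 events, and accrual over 2.5 years with about half in the last six months (Protocol 9.1).
- Discontinuation of 1% per year (Protocol 9.1 and SAP 8.2.1).
- Check on the inputs: 4 × (1.960 + 1.282)² / (ln 0.75)² = 508 events, which reproduces the protocol's figure.
- The first randomization date is not given. The original protocol is dated 26 August 2013, so follow-up to 01 November 2016 is at most 1,163 days, or 3.18 years. Cuts at 2.5, 3.0 and 3.18 years are shown.

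**Step 3. Closed-form size of the 8.1.1.1 population.** With event hazard λ (0.027 on placebo, 0.75 × 0.027 = 0.02025 on bococizumab), discontinuation hazard δ and available follow-up τ:

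- Probability of leaving event-free before the cut: δ/(δ + λ) × [1 − exp(−(δ + λ)τ)].
- Expected added events per subject, with placebo risk after leaving: ∫₀^τ δ exp(−(δ + λ)s) × [1 − exp(−0.027(τ − s))] ds.

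These are averaged over entry times (half uniform on 0 to 2 years, half uniform on 2 to 2.5 years) and summed over 5,500 subjects per arm.

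**Step 4. Hazard ratio shift.** This comes from 200 simulated trials per scenario with 100 imputations each. The model has exponential event and discontinuation times, a placebo-arm Weibull without covariates, parameters drawn from their estimated distribution, an unstratified Cox model and Rubin pooling.

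| Discontinuation | Cut (years) | Subjects imputed | Events added | Mean HR before → after | Mean shift |
|---|---|---|---|---|---|
| 1%/yr (SAP) | 2.5 | 93.8 | 1.91 | 0.7580 → 0.7600 | +0.0020 |
| 1%/yr (SAP) | 3.0 | 146.8 | 3.50 | 0.7665 → 0.7685 | +0.0020 |
| 1%/yr (SAP) | 3.18 | 166.1 | 4.26 | 0.7511 → 0.7536 | +0.0024 |
| 5%/yr (assumed) | 2.5 | 455.4 | 9.31 | 0.7548 → 0.7639 | +0.0091 |
| 5%/yr (assumed) | 3.0 | 709.0 | 17.01 | 0.7503 → 0.7610 | +0.0106 |
| 5%/yr (assumed) | 3.18 | 800.0 | 20.67 | 0.7527 → 0.7640 | +0.0113 |

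At 1% per year the Monte Carlo standard error of the mean shift is 0.0001, and the central 95% of single-trial shifts lies between −0.0003 and +0.0046 across the three cuts. The 5% rate is a stress case with no source in the documents.

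**Step 5. The three readings compared.**

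- Censored at the cut (ordinary meaning): in every simulated trial, 0 events added, no follow-up time changed, and no change in the log hazard ratio.
- Premature discontinuers (8.1.1.1): the table above.
- Anyone censored without an event (loose reading of 8.2.1): imputed data sets identical to the second reading in all 1,200 trials, because subjects censored at the cut contribute nothing.

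**The case against.** The best defence is that the intent can be recovered. Section 8.1.1.1 is explicit, the rationale in 8.2.1 speaks of premature discontinuation, and a truncation rule is pointless unless some imputed subjects were censored before the cut. The change summary in SAP 1.1, used here only to show intent, points the same way: "Multiple imputations for the primary endpoint were modified to impute for all subjects who discontinued from study prior to the date of program discontinuation". Of the three readings, two agree numerically and the third defeats itself. An analyst who got 100 identical data sets would probably notice. The shift at the documented 1% per year is about 0.002.

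Most of this stands as an argument about size and about which correction to make. It does not remove the conflict. The sentence in 8.2.1 that says who is imputed still differs from 8.1.1.1, and the SAP does not say which governs. Relying on someone noticing an empty result after the data are in does not replace a stated population.

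Two further points are fair. First, the figures are illustrative: actual enrolment and follow-up are not in the documents, covariates and stratification were left out, and the model has only two kinds of censoring. The agreement between the second and third readings might not hold for subjects whose last contact precedes the cut without a recorded discontinuation. Second, 8.1.1.1 has no date limit, so correcting 8.2.1 alone leaves a small textual difference. That difference is harmless numerically, because anyone who leaves on or after 01 November 2016 is truncated to the same record.

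**Conclusion.** The concern holds. The SAP gives two populations for one analysis, and the version in 8.2.1 rests on an undefined term that does not fit its own rationale. On the ordinary meaning, the only informative-censoring analysis in 8.2.1 that yields a hazard ratio adds nothing and reproduces the primary Cox result exactly. That conclusion follows from the conditional draw and the truncation rule alone.

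The cost of the error is modest. Under the stated assumption, "It is assumed that there will be a premature study discontinuation rate of 1% per year", the intended analysis would move the hazard ratio by about +0.002. At an assumed 5% per year it would move by about +0.009 to +0.011. These are orders of magnitude that rest on the planning inputs and on cuts of 2.5 to 3.18 years. The primary log rank test, its alpha of 0.04898 and the decision rule in SAP 4.2 are not affected. It should still be corrected, because the analysis exists to show what happens if dropout matters and as written it may not do so.

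**What to change.** Before unblinding, delete the term *administratively censored* from SAP 8.2.1 and define the imputed group as surviving, event-free subjects who left the study prematurely, before 01 November 2016. Keep the conditional draw and the truncation at that date. Adding the same date to the sentence in 8.1.1.1 would make the two sections agree word for word; this is tidy but not essential.

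The cost is one phrase in 8.2.1, or two if the date is also added to 8.1.1.1. No further data, analyses, sample size or alpha changes are needed.
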